Brief Summary	
The proposed study will examine the feasibility, acceptability, safety, effectiveness, and cost of an Accessible Care intervention for engaging people who inject illicit drugs (PWID) in hepatitis C care. Accessible Care for PWID is low-threshold care provided in programs designed specifically for PWID where they can comfortably access care without fear of shame or stigma. Accessible Care will be provided by co-locating a hepatitis treatment provider, together with a Hepatitis C Care Coordinator (HCCC), on-site at our collaborating needle exchange program. The proposed study will compare the effectiveness of Accessible Care with Usual Care (referrals to existing services) in facilitating linkage, engagement, and retention of PWID in care for hepatitis C, addiction, and HIV prevention. Our primary outcome is sustained virologic response, which constitutes virologic cure. Substance use and HIV and HCV risk behaviors are secondary outcomes. The Specific Aims of this study are to compare active PWID receiving Accessible Care or Usual Care on the following outcomes: 1. Hepatitis C Outcomes: (1a) Linkage and engagement in hepatitis C care, (1b) Successful hepatitis C treatment, (1c) Safety of hepatitis C treatment, and (1d) Rates of reinfection. 2. Substance use outcomes 3. Reductions in self-reported HIV and HCV risk behaviors. As all-oral regimens become available to patients who do not inject drugs, the substantial health disparities in hepatitis C already evident will become worse, as the haves are cured and the have-nots are not. Data are needed on effective methods to provide successful antiviral therapy to the core population affected by the epidemic, persons who are currently using illicit drugs, so that they, too, may benefit. Treatment can also help end the HCV epidemic by preventing onward transmission, but only if we have effective models for delivering treatment to people actively injecting drugs.

Phase	Clinical study phase 4
Objectives	The proposed study will compare the effectiveness of Accessible Care with Usual Care in facilitating linkage, engagement, and retention of PWID in care for hepatitis C, addiction, and HIV prevention.
Methodology	Open label; Randomized control
Endpoint	Our primary outcome is sustained virologic response (SVR), which constitutes virologic cure. Substance use and HIV and HCV risk behaviors are secondary outcomes.
Study Duration	4 years
Participant Duration	52 to 144 weeks
Duration of IP administration	N/A
Population	500 men and women, age >/= 18 who have injected drugs in the last 90 days.
Study Sites	Lower East Side Harm Reduction Center
Number of participants	500 participants all enrolled at the Lower East Side Harm Reduction Center

Description of Study Agent/Procedure	The research will be investigating a new model of Hepatitis C care delivery, 'Accessible Care'. Accessible Care is low-threshold care provided in programs designed specifically for PWID, in community-based locations where they can comfortably access care without fear of shame or stigma.
Reference Therapy	Accessible Care intervention will be compared to referral of hepatitis C infected patient to existing hepatitis C treatment sites (clinics and hospitals).
Key Procedures	Blood draws that are considered standard of care for hepatitis C treatment will take place as part of the study.
Statistical Analysis	We will compare the frequency of four hepatitis C treatment endpoints in the two arms in an intent-to-treat fashion, in order to evaluate the hypotheses that PWID in the intervention arm will be more likely than those in the control arm to begin, adhere to, complete, and achieve virologic responses to antiviral treatment for hepatitis C. The four endpoints will be defined as follows. Antiviral treatment initiation will be defined as taking the first dose of antiviral medication within 3 months of randomization. Adherence to antiviral treatment will be assessed by self-report and calculated as a percentage of prescribed doses. Treatment completion will be defined as taking the prescribed medications for the entire prescribed treatment duration. Sustained virologic response (SVR) will be defined as testing HCV RNA negative 12 weeks after treatment completion, the standard definition.

Schematic of Study Design

1 Key Roles

NYU:

[name] will be involved in the development of survey instrument and will be the lead clinician providing HCV care on-site at Lower East Side Harm Reduction Center. Participants randomized to the 'Accessible Care' arm of the research study will be offered on-site Hepatitis C treatment, with [name] being the primary medical provider. His study-related tasks will include:

1. obtaining a detailed medical history
2. performing a thorough physical examination
3. performing venopuncture to obtain laboratory specimen
4. discussing hepatitis C treatment options

Obstacles to engaging active PWID in care include their competing priorities (e.g., legal, financial, interpersonal, drug-related, housing), more pressing medical or social problems, comorbid psychiatric illness, addiction, fear of stigma, and historically poor relations with health care providers. Other barriers exist at the provider, healthcare system, and structural levels. >

2.2 *Name and Description of the Investigational Agent*

Accessible Care for PWID is low-threshold care provided in programs designed specifically for PWID, in community-based locations where they can comfortably access care without fear of shame or stigma. In collaboration with community-based organizations providing services to PWID in the South Bronx, East Harlem, and the Lower East Side of Manhattan, we developed an Accessible Care program and found that we could effectively treat both hepatitis C and addiction in a sample of PWID recruited from community-based settings who were actively using illicit drugs. By reducing illicit drug use and providing effective HIV and HCV prevention, the intervention reduced HIV risk behavior as well — a finding supported by a low HCV reinfection rate in follow-up.

The proposed study will compare the effectiveness of Accessible Care with Usual Care in facilitating linkage, engagement, and retention of PWID in care for hepatitis C, addiction, and HIV prevention.

2.2.1 *Preclinical Data*

N/A

2.2.2 *Clinical Data to Date*

In a single arm pilot study conducted by our team we treated 53 participants at a community based syringe service program in Washington Heights and found high rates of sustained virologic response of 91%.

2.2.3 *Dose Rationale (if applicable)*

N/A

2.3 Rationale

PWID are less likely to engage in HCV care through existing models of care delivery. Obstacles to engaging active PWID in care include their competing priorities (e.g., legal, financial, interpersonal, drug-related, housing), more pressing medical or social problems, comorbid psychiatric illness, addiction, fear of stigma, and historically poor relations with health care providers. Other barriers exist at the provider, healthcare system, and structural levels.

2.4 Potential Risks & Benefits

2.4.1 Known Potential Risks

Risk of social harm:

Participants may feel uncomfortable responding to questions about your medical conditions, their feelings, their drug use, or their sexual behaviors. Some of the questions are about topics that may make them feel guilty, anxious, or embarrassed.

Risk of drawing blood:

Drawing participant blood could cause pain, swelling, bruising, light-headedness, or, rarely, infection at the place where your blood was drawn.

Each of these potential risk are low risk, and in our the potential gain outweighs the risk.

2.4.2 Known Potential Benefits

People who inject drugs are the risk group most likely to be infected with HCV, and the least likely to be offered treatment. This study will offer important insights into the feasibility, safety and efficacy of treating active drug users using a co-located model of care designed with their needs in mind. Identifying effective ways to approach HCV treatment in this marginalized population will improve overall health and quality of life and reduce the spread of this disease. Participation in the study may benefit participants by eliminating the hepatitis C virus or halting the progression of this disease. Subjects may also benefit from the discontinuation of illicit drug use through our treatment model and improved health status and quality of life. Serious adverse events related to HCV antiviral treatment are uncommon. Should they occur the close monitoring structure allows early detection and intervention and the timely provision of expert medical care. Given the low risk presented by participation in this study, the risk/benefit ratio is very favorable.

3 Objectives and Purpose

3.1 Primary Objective

The proposed study will compare the effectiveness of Accessible Care with Usual Care in facilitating linkage, engagement, and retention of PWID in care for hepatitis C, addiction, and HIV prevention.

Hepatitis C Outcomes

Linkage and engagement in hepatitis C care, assessed as (a) stated interest in hepatitis C treatment evaluation, (b) attendance at an initial visit with a hepatitis provider, (c) completion of a medical evaluation for antiviral treatment, and (d) attendance at two visits with a hepatitis treatment provider within 3 months. Successful hepatitis C treatment, defined as (e) beginning antiviral treatment, (f) adherence to antiviral treatment, (g) completion of antiviral treatment, and (h) sustained virologic response, the primary

outcome. We will also describe (i) the reasons for any participants not reaching treatment endpoints (a)–(h) according to staff and participant report, and (i) the costs of the intervention in each arm. Safety of hepatitis C treatment measured by the frequency of side effects, adverse events, and doselimiting toxicity, since these rates haven't been reported in PWID receiving all-oral regimens. Rates of reinfection in active PWID who have achieved SVRs with antiviral therapy for hepatitis C. Reinfection is one of the primary reasons cited for withholding antiviral treatment from PWID.

Substance use outcomes

Substance abuse treatment entry and retention in each arm 3, 6, and 9 months after randomization. Reductions in substance use during follow-up assessed as (a) self-reported frequency of drug injection, and (b) self-reported percentage of days of drug or alcohol use, and (c) urine toxicology.

4 Study Design and Endpoints

4.1 Description of Study Design

The proposed study will evaluate the effectiveness of Accessible Care (AC) for engaging and retaining PWID in care for hepatitis C, as compared with Usual Care (UC). A sample of 300 PWID with chronic hepatitis C will be recruited from the Lower East Side Harm Reduction Center, our community-based partner, and offered enrollment in a longitudinal study in which they will be randomized 1:1 to receive AC or UC. Participants will be given an appointment with a Hepatitis C Care Coordinator (AC) or referrals to existing community resources (UC), according to their study arm. To assure that any observed effects can be attributed to the intervention and not to differences in insurance, transportation, or physician characteristics, study participants in both arms will receive assistance signing up for health insurance (Medicaid); transit fare (MetroCards) as needed for appointments; and access to the same study physicians at the Weill Cornell Medical Center (WCMC) Center for the Study of Hepatitis C.

All patients who choose to receive antiviral treatment and have no contraindications will undergo state-of-the-art antiviral therapy according to standard clinical protocols. Study physicians are committed to caring for people who use drugs without shaming, blaming, or stigmatizing them or withholding care on the basis of arbitrary requirements for abstinence from substance use.

Participants in both arms will be interviewed at baseline and 3, 6, and 9 months after randomization. To assure retention in follow-up and reduce differential attrition, all patients will be seen monthly for a check-in to update contact information, as we have done in previous research. Outreach workers will help retain participants in the study by reminding them of upcoming appointments and searching for those lost to follow-up. Participants in both arms will be asked monthly if they've started antiviral therapy and those receiving antiviral therapy will be interviewed monthly while on therapy to assess adherence and side effects. Patients will receive cash stipend for each study interview or monthly check-in.

Clinical data, including medication start and stop dates and doses, viral RNA levels, other laboratory test results, and adverse events, will be abstracted electronically from the WCMC electronic medical record or by requesting records from other facilities. The effectiveness of AC will be assessed and compared with Usual Care through formal intent-to-treat analyses comparing study endpoints. Semi-structured qualitative interviews will also be conducted with a theoretically sampled group of 60 participants 6 months after randomization, including some who dropped out or did not pursue treatment, to provide contextualized data on how the intervention worked, or didn't, and its strengths and weaknesses. All patients achieving SVR will be followed up with quarterly HCV RNA testing for the duration of the study to detect reinfections. The cost of the intervention in each arm will be estimated as a key component of assessing the feasibility of the interventions. While our program requires intensive effort by intervention staff, we anticipate that that the incremental cost of this effort will be well within the range of the current cost of hepatitis C treatment.

Aim 1c. Cost of intervention: The HCCC and the Clinician will log time spent providing services, excluding research activities. Costs will be assigned to staff time based on prevailing national wage rates. Patient time costs will also be estimated based on time spent with staff members and will be valued based on the minimum wage because most patients are likely to be unemployed. We will describe patient-reported health care visits, employment, and incarceration that will be used as inputs to future cost or cost-effectiveness studies.

Aim 1d. Safety: Because concern about side effects has been cited as a reason not to treat PWID for hepatitis C, and because experience with these drugs in PWID has not been reported, we will report prospectively collected data on safety outcomes on all participants who receive antiviral therapy. All treatment-emergent side effects (e.g., fatigue, headache, nausea, insomnia, irritability, anorexia, diarrhea, constipation, etc.) will be tabulated, as will adverse events, including abnormalities in serum bilirubin, liver enzymes, infections, hospitalizations, and deaths), and any adverse effects requiring treatment discontinuation, according to OHRP152 and NIH153 guidelines. We will describe the frequency of side effects, adverse events, and treatment-limiting outcomes, among all study participants who received at least one dose of antiviral medication. If numbers permit, we will compare the rates in the two arms to see whether AC influences perceived side effects.

Aim 1e. Reinfection: We will report reinfection rates in all patients in both arms who achieve SVR using time-to-event methods. If 150 participants initiate antiviral therapy (50% overall) and 120 (80%) of those achieve SVR, with 2%/month attrition (21.5%/yr), we will have 198.3 person-years of follow-up when data collection is concluded, enough for a reasonably robust estimate.

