10. Within 6 months of enrolling in the study, participants will have a one-on-one meeting with a hepatitis C study coordinator to review harm reduction practices. This discussion will include discussions on prevention of hepatitis C transmission and re-infection, ways to engage in safe injection practices and avoid cross-contamination of injection equipment while injecting with others.
11. Data from participants' clinical medical records will be entered into our research database during the course of your treatment by a members of the research staff. These data include, but are not limited to, hepatitis C genotype, hepatitis C viral load, fibrosure results(looking for signs of cirrhosis), HIV antibody, sustained virologic response (defined as no detectable hepatitis C virus 12 weeks after completing therapy), and any side effects or adverse effects you experience during therapy

If participants agree to take part in this study and are assigned to Group B, participants will have the following tests and procedures:

Group B –Usual Care Group (Hepatitis Care at usual locations in the community): If assigned to this group, participants will participate in research visits but not receive hepatitis care or treatment at the Lower East Side Harm Reduction Center as part of the study. Participants can obtain care and treatment for hepatitis C at the usual locations in the community.

Research Visits (every 3 mos): Information that will be collected for the study will consist of (1) detailed questionnaires, and (2) one or more extra blood tests. The details of the study are as follows:

1. Questionnaires will be administered every three months for up to 12 months, independent of whether participants receive treatment for your hepatitis C, with questions about their demographics (e.g., age, gender, race), their alcohol and drug use history and practices, sexual practices and experience with health care.
2. One teaspoon of your blood will be drawn and sent to New York Presbyterian Hospital –Weill Cornell Translation Science Center where it will be processed and stored for potential future testing of characteristics of your Hepatitis C virus.
3. Human Immunodeficiency Virus (HIV) testing as described above will be offered at a research visit every 6 months to those participants who previously tested negative for HIV.

Hepatitis Care and Treatment:

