4. Participants will be referred to a hepatitis C case manager (funded through the New York City Department of Health Check Hep C Program), on site at their harm reduction facility (Lower East Side Harm Reduction Center), who will assist participants with referral for hepatitis C care within the community.
5. If participants start treatment for hepatitis C during their time in the study, we will ask participants to give us permission to talk with their hepatitis C doctor so we can have access to their medical records and monitor how they are responding to treatment.
6. If participants achieve a sustained virologic response after completing hepatitis C treatment, which means that the treatment was successful, participants will be given an appointment to come back every three months to complete a study interview and be tested for hepatitis C, for up to 144 weeks after treatment completion, to find out whether they are still negative, or to see whether they get re-infected.

QUALITATIVE INTERVIEWS During the study, we may ask participants to take part in an interview about their experiences related to hepatitis C treatment. This will last about 60-90-minutes. If participants choose to participate, the interview will be digitally audio-recorded. If participants are selected for this interview we will ask participants about: health care and hepatitis C-related healthcare experiences, alcohol and drug use, injection risk behaviors and sexual practices. We will ask participants how these changed, if they did, during their taking part in the study.

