9.2 Statistical Hypotheses

Specific Aim 1: Hepatitis C Outcomes.

Hepatitis C treatment engagement. We will assess the proportion of patients in each arm who (a) referred to a hepatitis C treatment provider, (b) attend an initial visit with a hepatitis treatment provider, and (c) complete a medical evaluation for antiviral treatment, including a history, physical examination, and laboratory evaluation. Proportions with 95% confidence intervals (CIs) calculated using the exact binomial method will be reported. Persons who are lost to follow-up will be considered in each analysis as not having reached the outcome, according to intent-to-treat principles.

Hepatitis C treatment success. We will compare the frequency of two hepatitis C treatment endpoints in the two arms in an intent-to-treat fashion, in order to evaluate the hypotheses that PWID in the intervention arm will be more likely than those in the control arm to begin treatment and achieve virologic responses to antiviral treatment for hepatitis C. The two endpoints will be defined as follows. Antiviral treatment initiation will be defined as physically receiving the first dose of antiviral medication. Sustained virologic response (SVR) will be defined as testing HCV RNA negative 12+ weeks after treatment completion.

Cost of intervention: The HCCC and the Clinician will log time spent providing services, excluding research activities. Costs will be assigned to staff time based on prevailing national wage rates. Patient time costs will also be estimated based on time spent with staff members and will be valued based on the minimum wage because most patients are likely to be unemployed. We will describe patient-reported health care visits, employment, and incarceration that will be used as inputs to future cost or cost-effectiveness studies.

Reinfection: We will report reinfection rates in all patients in both arms who achieve SVR using time-to-event methods. If 150 participants initiate antiviral therapy (50% overall) and 120 (80%) of those achieve SVR, with 2%/month attrition (21.5%/yr), we will have 198.3 person-years of follow-up when data collection is concluded, enough for a reasonably robust estimate.

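### Patient time is costed only from time with staff, so travel and waiting are left out of both arms, outside Usual Care time has no named source, and the per-arm patient-time costs are not comparable

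*Combined protocol and SAP*

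**What the plan says.** Section 4.2.1, Aim 1c, names two time-loggers: "The HCCC and the Clinician will log time spent providing services, excluding research activities". It then says: "Patient time costs will also be estimated based on time spent with staff members", valued at the minimum wage. Section 9.2 repeats both statements and adds no further time component. Patient-reported health care visits are to be described, but as inputs to later cost studies.

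The arms differ in where care happens. In 4.1 the HCCC appointment belongs to Accessible Care, while Usual Care receives referrals. Section 7.1 puts Accessible Care visits at the harm reduction center. For Usual Care it says: "Participants can obtain care and treatment for hepatitis C at the usual locations in the community", with help from an on-site case manager paid for by a city program. Section 4.1 also gives both arms "access to the same study physicians at the Weill Cornell Medical Center (WCMC) Center for the Study of Hepatitis C". It foresees travel as well, and offers each arm "transit fare (MetroCards) as needed for appointments".

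Cost in each arm is a listed outcome in 3.1, and 4.1 calls it a key part of judging feasibility. No formal between-arm comparison of patient time is specified.

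**The concern.** Sparing patients a journey and a wait is one of the plainest ways in which co-located care could help them. A rule based on staff contact cannot see that saving in either arm. It also depends on logs kept by two people who are central to Accessible Care and may see few Usual Care patients.

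The result would be two patient-time figures that measure different shares of the true burden. Printed side by side under a cost-in-each-arm objective, they will be read as a comparison whether or not a test is attached. Travel and waiting that are not asked about during follow-up are hard to recover afterwards, so deferring fuller costing to future studies does not solve the problem.

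**Working it through.** The documents give no figure for minutes, wage or patient-time cost, so there is nothing of the plan's own to reproduce. The check has two parts.

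**1. What the rule covers**

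| Component | Accessible Care | Usual Care |
|---|---|---|
| HCCC contact | Logged | No HCCC appointment in this arm |
| Clinician contact | Logged | Possibly logged if a shared study physician is seen; no source otherwise |
| Case manager contact | Not part of the arm's described care | Not named as logging |
| Travel and waiting | Not counted | Not counted |

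**2. Direction and size (illustration only)**

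Inputs from the documents:
- Uptake of 66% v 50%. This is the power example in 9.4; with 150 per arm it gives 80.5% power against the stated 80%. It is not a forecast.
- Seven clinical visits per treated Accessible Care patient, from 7.1: evaluation, results, treatment weeks 2, 4 and 12, and 4 and 12 weeks after treatment.

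Assumptions: the same seven visits in Usual Care, clinical visits by treated patients only, all Accessible Care contact logged, and every minute value below.

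Let A be the uncounted minutes per Accessible Care visit (travel plus waiting). Let U be the uncounted minutes per Usual Care visit (travel plus waiting, plus contact if it is not logged). Per randomised patient, the rule overstates the Accessible Care minus Usual Care difference by

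7 × (0.50 × U − 0.66 × A).

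This is positive when U > (0.66 / 0.50) × A = 1.32 × A. HCCC time cancels, because it is counted both under the rule and in full.

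Mid case: A = 20 + 20 = 40; Usual Care travel plus waiting = 45 + 45 = 90; contact 30.
- Usual Care contact not logged: U = 120, and 7 × (60 − 26.4) = 235.
- Usual Care contact logged: U = 90, and 7 × (45 − 26.4) = 130.
- Difference under the rule, not logged: (0.66 × 7 × 30 + 120) − 0 = 259.
- Difference in full: (0.66 × 7 × 70 + 120) − 0.50 × 7 × 120 = 443 − 420 = +23.

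All cases are in minutes per randomised patient. Paired values are for Usual Care contact not logged / logged, and entries are rounded separately.

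| Case | Contact per visit | Travel + wait, Accessible / Usual | HCCC | Difference, rule | Difference, full | Overstatement |
|---|---|---|---|---|---|---|
| Low | 20 | 25 / 50 | 60 | 152 / 82 | 23 | 130 / 60 |
| Mid | 30 | 40 / 90 | 120 | 259 / 154 | 23 | 235 / 130 |
| High | 45 | 60 / 150 | 180 | 388 / 230 | −17 | 405 / 248 |
| Equal travel and wait | 30 | 90 / 90 | 120 | 259 / 154 | 254 | 4 / −101 |
| Accessible Care longer | 20 | 105 / 35 | 120 | 212 / 142 | 505 | −293 / −363 |

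The first three rows assume that co-location shortens travel and waiting. The last two do not.

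**The case against.** The case for leaving the plan alone has several parts.

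- **The omission applies to both arms.** This stands. Accessible Care patients also travel and wait: transit fare is offered to both arms, and 5.4 allows recruitment through other organisations and in public places. But the omission cancels only if uptake-weighted uncounted time is equal, and nothing in the documents suggests that it is.
- **Usual Care contact is not certain to be zero.** This also stands. The text says staff members without qualification, and Usual Care patients may see the shared physicians. Logging that contact would still leave travel, waiting and visits elsewhere uncounted.
- **No between-arm comparison of patient time is planned.** This is correct. The incremental cost mentioned in 4.1 concerns intervention staff effort, set against the cost of treatment. Costs reported by arm still invite the comparison.
- **Patient-reported visits are collected.** They are, but they are reserved for later studies, and no travel or waiting item is described.

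A reader might go further and infer that the rule counts Accessible Care in full and Usual Care as nothing, or that the true difference has the opposite sign. The documents support neither. Accessible Care travel and waiting are missing too, and 7.1 has research staff, who are not named loggers, drawing blood at treatment visits.

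A sign change depends on assumed hours. With 99 v 75 treated patients (66% and 50% of 150), seven visits at 1 hour on site and 2 hours off site give 693 v 1,050 hours. At 1 hour each they give 693 v 525. Ignoring HCCC time, a flip needs total Usual Care time per visit above 1.32 times that of Accessible Care; counting HCCC time raises the bar. The mid case does not flip.

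**Conclusion.** The point holds as a matter of comparability. The rule omits travel and waiting in both arms and names no source for Usual Care time with outside providers or the case manager, so the two patient-time costs cannot be set against each other. They probably overstate the relative burden of Accessible Care: by 60 to 405 minutes per randomised patient across the assumed co-location cases. That range rests on assumed minutes, equal visit counts and the 66% v 50% example. With equal or longer Accessible Care travel and waiting, it becomes +4 to −363. Bias against Accessible Care is therefore likely but not established, and a sign reversal is only possible.

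This concerns one component of a descriptive cost aim. The SVR primary analysis is unaffected. It is a cheap improvement that should be made while the data can still be collected.

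**What to change.** In 4.2.1 Aim 1c and 9.2, define patient time as visit, waiting and travel time for hepatitis C visits, on site or off site, in both arms, valued at the same wage. Collect it by adding visit-duration, travel and waiting items to the patient-reported health-care-visit questions in the existing three-monthly interviews. Show staff-contact time as a secondary line, and state whether Usual Care contact with the shared physicians is in the log.

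If these items are not collected, report staff-contact time only as intervention delivery cost and draw no between-arm conclusion on patient time.

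The cost is wording in two sections, a few added interview items, and recall error in self-reported durations over three months.
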